7.7.1 Rescue medicine

The study site will supply rescue medication that will be obtained locally upon local recommendation.

The use of established anti-malarial drug combination per WHO recommendations (6) and per local regulations and the choice of the best therapeutic option is left at investigator's decision.

The use of rescue medications is allowed as soon as

- vomiting occurs during FQ dosing or after FQ dosing but before OZ439 administration,
- vomiting occurs within 35 minutes after OZ439 re-dosing (see Section 7.1.1.2), or
- there is evidence of treatment failure (see definition below).

If no rescue medication is administered before Day 28, it will be administered on Day 28.

Treatment failure is defined according to WHO recommendations (2) as follows:

Early treatment failure (one the following)

- danger signs or severe malaria on Day 1, 2, or 3 in the presence of parasitemia;
- parasite count on Day 2 higher than on Day 0, irrespective of axillary temperature;
- parasitemia on Day 3 with axillary temperature ≥ 37.5 °C;
- parasite count on Day $3 \ge 25\%$ on Day 0.

Late clinical failure

- danger signs or severe malaria on any day between Day 4 and Day 28 in the presence of parasitemia, without previously meeting any of the criteria of early treatment failure;
- presence of parasitemia and axillary temperature ≥37.5°C (or history of fever) on any day between Day 4 and Day 28, without previously meeting any of the criteria of early treatment failure.

Late parasitological failure

• presence of parasitemia on any day between Day 7 and Day 28 and axillary temperature <37.5°C, without previously meeting any of the criteria of early treatment failure or late clinical failure.

Before giving a rescue therapy before Day 28, where possible:

- a PK (OZ439 and FQ) sample should be taken
- blood films, parasite genotyping, RT-qPCR, and qPCR must be taken

Following administration of rescue therapy before Day 28, patients should be managed according to local standard of care practices. Safety data, parasitemia (blood films), and PK data should continue to be collected in the e-CRF, according to the study schedule, and up to the end of the study (Day 28) even if re-emergence is confirmed.

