
- Development of danger signs or symptoms of complicated/severe malaria on Day 1, Day 2 or Day 3, in the presence of parasitemia (reported as Term='Complicated Malaria' by the investigator in the 'Adverse Event' form and reported in the e-CRF dedicated form "Malaria Signs and Symptoms") concomitant to at least one positive parasitemia. Considering that the drug cannot be active before 24h, a severe malaria presenting between 0h and 24h is highly suspect of wrong inclusion of the patient.- Parasitemia on Day 2 higher than baseline parasitemia count (irrespective of body temperature)- Parasitemia on Day 3 with axillary temperature of $\geq 37.5^{\circ}\text{C}$- Parasitemia on Day 3 $\geq 25\%$ of baseline parasitemia count
LCF is defined as one of the following, without previously meeting any of the ETF criteria :

- Development of danger signs or severe malaria after Day 3 in the presence of parasitemia (reported as Term='Complicated Malaria' by the investigator in the 'Adverse Event' form and reported in the e-CRF dedicated form "Malaria Signs and Symptoms") concomitant to at least one positive parasitemia.- Presence of parasitemia and axillary temperature $> 37.5^{\circ}\text{C}$ on any day from Day 4 to Day 28, without previously meeting any of the criteria of early treatment failure
LPF

- Presence of parasitemia on any day from Day 7 to Day 28, and axillary temperature $< 37.5^{\circ}\text{C}$, without previously meeting any of the criteria of ETF or LCF

Criterion

ACPR

- Absence of parasitemia on Day 28 irrespective of axillary temperature without previously meeting any of the criteria of ETF or LCF or LPF, and without previous rescue therapy start. Rescue therapy start without previous WHO criteria can be due to: investigator decision (classified as failure or deviation based on case by case clinical review, see [Section 2.3.2.2](#)), major vomiting or severe malaria at Day 0 (both classified as deviation, see [Section 2.3.2.2](#)), other species infection.

The following definitions will also be considered regarding efficacy evaluation:

Re-emergence / Recurrence (recrudescence and re-infection): The appearance of asexual parasites after clearance of initial infection irrespective of genotype.

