2.1.4.2.8 Fever clearance time (FCT)

FCT is the time from start of study drug administration until temperature remained below 37.5°C.

Fever is defined by a body temperature $\geq 37.5^{\circ}\text{C}$ for axillary temperature or by a body temperature $\geq 38^{\circ}\text{C}$ for other routes of measurement.

Timing to consider rules will be similar to what it is described in [Section 2.1.4.2.3](#). The FCT is the post-dose timing associated to the first vital sign assessment as defined above.

In case the FCT is not observed or confirmed before withdrawn (for any reason) or before start of rescue therapy, then the FCT will be censored at the time of the last vital sign assessment (using the post-dose timing above defined) before withdrawn or rescue therapy start, whichever comes first.

FCT is not applicable for patients with baseline body temperature $< 37.5^{\circ}\text{C}$ for axillary temperature (or $< 38^{\circ}\text{C}$ for other routes of measurement) or missing.

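### SAP Table 1 leaves a positive film at exactly 37.5 °C on Days 4–28 outside both late failure classes, although protocol 7.7.1 counts it as late clinical failure

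*SAP*

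**What the plan says.** Protocol 7.7.1 gives one LCF criterion as "presence of parasitemia and axillary temperature ≥37.5°C (or history of fever) on any day between Day 4 and Day 28" and LPF as "presence of parasitemia on any day between Day 7 and Day 28 and axillary temperature <37.5°C". Protocol 10.3.1.1 defines ACPR as a negative Day 28 film without earlier failure by these criteria.

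SAP Table 1 words the matching LCF criterion as "Presence of parasitemia and axillary temperature $> 37.5" °C (the dollar sign is a typesetting remnant; the condition is strictly above). It applies "on any day from Day 4 to Day 28, without previously meeting any of the criteria of early treatment failure", and the history-of-fever alternative is gone. LPF remains "Presence of parasitemia on any day from Day 7 to Day 28, and axillary temperature" below 37.5 °C.

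Elsewhere the SAP uses the inclusive limit. The Day 3 criterion for early treatment failure (ETF) in the same table is 37.5 °C or more, and section 2.1.4.2.8 defines fever as an axillary reading of 37.5 °C or more. SAP 1.5 says that no amendment changed the statistical section. SAP 1.6, which lists the SAP's own changes, does not mention LCF.

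**The concern.** The protocol's two late criteria meet at 37.5 °C, so from Day 7 they cover every temperature. The SAP's two criteria leave out one value. Protocol 9.4.2 has axillary temperature recorded to one decimal place, so 37.5 °C is an ordinary reading.

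The gap lies in the classification behind the primary endpoint. The SAP defines treatment failure as ETF, LCF or LPF, and it sub-classifies by genotype only LCF from Day 7 and LPF. A case in the gap reaches neither step. The rule also conflicts with the SAP's own imputation: with concomitant malaria fever, which includes 37.5 °C, a missing film is set to positive, yet that temperature does not count towards LCF.

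The planned number of failures is small, so the coding of single patients can matter to the Wald test. The trial is open label, so it is better to settle such cases by a fixed rule than by later judgement.

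**Working it through.** **Step 1: the rules side by side.** I applied the fever and parasitemia criteria of each document to a positive film at 37.4, 37.5 and 37.6 °C, with and without a history of fever, on Days 3, 4, 5, 6, 7, 10, 14, 21 and 28. Danger signs, severe malaria and the parasite-count criteria for ETF were taken as absent.

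| Reading | Day | Protocol 7.7.1 | SAP Table 1 |
|---|---|---|---|
| 37.5 °C, any history | 3 | ETF | ETF |
| 37.4 °C, no history | 4–6 | none | none |
| 37.4 °C, no history | 7–28 | LPF | LPF |
| 37.4 °C, history of fever | 4–6 | LCF | none |
| 37.4 °C, history of fever | 7–28 | LCF | LPF |
| 37.5 °C, any history | 4–28 | LCF | none |
| 37.6 °C, any history | 4–28 | LCF | LCF |

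At exactly 37.5 °C the documents disagree on all 8 late days checked. Below 37.5 °C, dropping history of fever removes a failure only on Days 4–6. From Day 7 the case is relabelled LPF, which is still a failure and still genotyped.

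**Step 2: how a 37.5 °C case is scored under SAP 2.1.4.1.**

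- *Rescued on Days 4–6.* It falls in the row for rescue without a prior WHO failure. Before Day 7 that row is a failure in both columns, so the score matches LCF before Day 7.
- *Rescued from Day 7 and before Day 28.* The same row now gives exclusion in the per-protocol column and failure in the mITT column. As LCF, a recrudescence would be a failure in both, while a reinfection would be excluded per protocol and a failure in mITT. The score therefore changes only for a recrudescence in the per-protocol column.
- *Not rescued, no later qualifying film, negative film on Day 28.* The ACPR definition is met on its face, so the patient could be scored a success.
- *First positive film on Day 28.* The film rules out ACPR, and no failure class applies. The rescue row cannot sensibly apply, because everyone not yet rescued receives rescue that day. The case has no row.

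**Step 3: which column applies.** The primary analysis uses the PK/PD efficacy population (SAP 1.6, 2.3 and 2.4.4). Section 2.3.5.1 starts from the PK and mITT populations but then lists reasons for non-evaluability that are exclusions only in the per-protocol column. The summary table at the end of SAP Appendix B labels the primary regression per protocol. Both point to the per-protocol column; neither states it.

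**Step 4: size.** Inputs: planned response rates of 72%, 81%, 91% and 97%, with 30 evaluable participants per arm (protocol Appendix 8).

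Planned failures = 30 × (0.28 + 0.19 + 0.09 + 0.03) = 30 × 0.59 = 17.7.

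The documents give no frequency for readings of exactly 37.5 °C. Assume a share q of failure visits; the expected number affected is at most 17.7 × q.

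| q (assumed) | Upper bound on expected failures affected |
|---|---|
| 1% | 17.7 × 0.01 = 0.18 |
| 3% | 17.7 × 0.03 = 0.53 |
| 5% | 17.7 × 0.05 = 0.89 |

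These are upper bounds, because the 17.7 includes ETF, LCF by danger signs, and rescued Day 4–6 failures, none of which changes score by this route.

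**The case against.** The strongest reply is that this is a slip of one sign. The rest of the SAP uses the inclusive limit, and Table 1 is presented as the WHO classification. A lost underline in the published copy cannot be wholly excluded, though the same table prints the inclusive sign correctly for ETF. A slip is plausible, but the rule would still be programmed as written, and a lost underline would not explain the missing history of fever.

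The SAP also has backstops. Table 1 lets clinical review class investigator-decided rescue as failure or deviation. Section 2.3.5.1 does not treat rescue for failure as judged by the investigator as a violation. Section 2.1.4 says that a genotypically identical parasite is a treatment failure, with no temperature condition. These may recover cases, but they conflict with the per-protocol row for rescue on or after Day 7, and the SAP does not say which prevails. For crude ACPR the objection stands for rescued patients, since rescue without a WHO failure is scored as failure in both columns.

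A reader might infer that true recrudescences drop out of the primary endpoint. The documents do not establish that. It requires rescue on or after Day 7, the per-protocol column, and no recovery at clinical review. A reader might also compute the chance of losing at least one failure as 1 − (1 − q)^17.7, which gives 16%, 42% and 60% for q of 1%, 3% and 5%. Those figures put every planned failure at risk and rest on shares that the documents do not support.

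**Conclusion.** The inconsistency is real and undeclared. As written, the SAP assigns no failure class to a positive film at exactly 37.5 °C on Days 4–28 without danger signs or severe malaria. The protocol calls it LCF.

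It would be too broad to say that such a film is no failure on any day: on Day 3 the reading is ETF, and danger signs or severe malaria with parasitemia remain LCF at any temperature. Below 37.5 °C, the loss of history of fever matters only on Days 4–6, and mainly for unrescued patients, because rescue before Day 7 is already scored as failure.

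The expected effect is below one patient: at most 0.2 to 0.9 of a failure, on an assumed 1–5% share. No effect on power or on the Wald test has been shown. The case for correction is that the primary endpoint should classify every patient by a stated rule, and this one does not.

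**What to change.** Before database lock, reconcile the LCF definition in SAP Table 1 with protocol 7.7.1. Either use the protocol's criterion for the analysis (37.5 °C or more, or a history of fever), so that LCF and LPF leave no gap from Day 7, or list and justify the change in SAP 1.6 and adjust LPF so that no temperature is left out. This concerns endpoint coding only, not when rescue is given.

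Add a sentence stating which column of the table in 2.1.4.1 governs the PK/PD efficacy population.

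The cost is one line in Table 1, one sentence elsewhere and the matching program change. The threshold needs no new data. For the history-of-fever part, check that it is recorded at the follow-up visits.

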7.4 BLINDING

Not applicable since this is an open label study using central randomization via IRT; the specific treatment to be taken by a participant will be assigned using IRT. The site will contact IRT prior to the start of study treatment administration for each participant.

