Based on N=10,000 simulations/arm and S=1000 simulations for the model parameters uncertainty, the results showed a PCR-corrected ACPR at Day 28 estimated at 72% (90%CI: [57% to 84%]) for FQ 400mg alone and 79% (90%CI: 67% to 87%) for FQ 600 mg alone for a baseline parasitemia greater than 3000 parasites/ μ L. Finally the FQ fixed dose of 400 mg was selected.

Part 2: Estimated power for various sample size of an OZ439 exposure-effect analysis, considering the fixed FQ dose, the 4 selected OZ439 dose levels (0, 300, 600, 1000 mg) and the selected baseline parasitemia

Simulation of clinical trials

Clinical trial simulations were used to simulate trials of 4 arms with a fixed dose of 400 mg FQ and 4 dose levels of OZ439 (0, 300, 600, and 1000 mg) for a baseline parasitemia greater than 3000 parasites/µL. FQ and OZ439 concentrations at Day 7 (168 h post dose) were simulated using log-normal distributions that were adjusted to concentrations obtained from the FQ PopPK model and from the OZ439 PopPK model in an African adult population (as in part 1), and were assumed to be slightly correlated. Truncated log-normal distributions were used to simulate baseline parasitemia greater than 3000 parasites/µL in log10Par/µL by a normal distribution: mean=4, SD=0.55, minimum=3.48; maximum=5.5 (minimum and maximum for the truncation). Day 28 PCR-corrected ACPR was simulated using a "hypothetical" model linking ACPR at Day 28 probability to FQ and OZ439 concentration at Day 7 and baseline parasitemia.

The "hypothetical" logistic regression model (eq 2, see below) used for simulations was a composite of the "PQP/OZ-ACPR28 model" built by MMV, modeling PCR-corrected ACPR at Day 28 probability (p) as a function of OZ439 and PQP concentrations at Day 7 and baseline log10-parasitemia, and of assumptions made on FQ efficacy, which were based on the results of part 1. Precisely, β FQ was fixed at 0.12 by calibration to get ~ 72% success ACPR at Day 28 for FQ 400 mg alone for a baseline parasitemia greater than 3000 parasites/ μ L, and the following parameters were extracted from the MMV model: α =3.23, β OZ439 = 0.73, and β BasePar = -1.27.

(eq 2)
$$log(p/(1-p)) = \alpha + \beta FQ.ConcD7FQ + \beta OZ439.ConcD7OZ + \beta BasePar.log10(BasePar)$$

Using all these assumptions, the PCR-corrected ACPR at Day 28 rates simulated in the 4 arms FQ 400 mg \pm OZ439 at 0, 300, 600 and 1000 mg were of 72%, 81%, 91%, and 97% for a baseline parasitemia greater than 3000 parasites/ μ L.

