Clinical trials analyses

Exposure-effect analyses of the simulated clinical trials were performed, consisting of a logistic regression model of exposure at Day 7 for both drugs, with baseline parasitemia as covariate, and the Day 28 PCR-corrected ACPR as response variable (as in eq 2 above). Significance of OZ439 concentration effect (βOZ439) was analyzed using a 2-sided alpha Wald test at 5%.

Overall, five thousand trial simulations were performed, and the power was deduced as the percentage of significant simulated trials. Results estimated that 30 evaluable participants per treatment arm will yield a power around 90% to detect an OZ439 concentration effect relation (in a population of patients with a baseline parasitemia greater than 3000 parasites/ μ L, for 4 arms FQ 400 mg + OZ439 at 0, 300, 600, and 1000 mg).

Around 15 % of early dropout is anticipated, consequently approximately 35 participants are to be included in each arm (to get 30 evaluable participants/arm) resulting in approximately 140 participants to be enrolled in the whole study.

Property of the Sanofi group - strictly confidential

Clinical Trial Protocol ACT14655 – artefenomel/ferroquine 13-Nov-2017 Version number: 1

A rather large uncertainty was attached to the models and to the different assumptions used to perform the simulations, so these results are approximate.

13-Nov-2017 Version number: 1

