In addition, except where otherwise specified, the following imputation rules will apply in case of missing or out of time window parasite count at a protocol scheduled time point, where the missing count occurs before rescue treatment start, before or on Day 28, or in absence of concomitant fever. In such cases, the missing parasitemia will be considered as:

- positive, if followed or preceded by positive parasitemia,
- negative, if preceded and followed by negative parasitemia,
- missing, if no parasite count available thereafter.

In above bullets:

- positive parasitemia means *P. falciparum* parasite count from thick film ≥ 1 parasite/ μ L, otherwise the parasitemia is negative.
- parasite count from thick film performed after rescue treatment start cannot be used for imputation of missing or out of time window parasite count.

- parasite count from thick film performed the day of rescue treatment start can be used for imputation because this is regarded as before rescue treatment.

In case of concomitant fever related to malaria event (fever is defined in [Section 2.1.4.2.8](#)), a missing parasitemia will be always considered as positive.

In case of missing (or out of time window) parasite count at successive protocol scheduled time points, the above imputations rules could be extended after endorsement of the imputations by the clinical team, otherwise the case will be classified as a deviation preventing evaluation of ACPR as listed in [Section 2.3.2.2](#). Cases of missing body temperature concomitantly with positive parasitemia (observed, or put in place of a missing parasite count as explained above) will be imputed, according to the same principle as for parasitemia imputations, after endorsement of the imputations by the clinical team, or will be classified as deviation.

Efficacy evaluation

Efficacy evaluation will use Early Treatment Failure (ETF), Late Clinical Failure (LCF), Late Parasitological Failure (LPF), and Adequate Clinical and Parasitological Response (ACPR) definitions given below.

Table 1 - Revised WHO classification of treatment failures in areas of intense malaria transmission

Criterion
ETF is defined as one of the following :

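### Open-label case review can class a pre-Day-7 rescue without WHO criteria, or a run of missing parasite counts, in or out of the primary analysis, with no masking or timing stated

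*SAP*

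**What the plan says.** On masking, Protocol 7.4 reads "Not applicable since this is an open label study using central randomization via IRT".

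SAP 2.1.4, Table 1, deals with rescue started without prior WHO failure criteria. Major vomiting and severe malaria at Day 0 are fixed as deviations. Investigator-decision rescue is instead "classified as failure or deviation based on case by case clinical review".

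For parasite counts missing at successive scheduled times, the imputation rules in the same section "could be extended after endorsement of the imputations by the clinical team"; otherwise the case becomes a deviation that prevents evaluation of ACPR.

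The outcome table in SAP 2.1.4.1 has a fixed row for rescue without WHO criteria, but only for cases not already classed as violations. In its Per Protocol column such a rescue is a failure before Day 7 and excluded from Day 7 on. A violation is excluded at any time. In the mITT column all of these are failures.

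The primary test uses the PK/PD efficacy population (SAP 2.3, 2.4.4). SAP 2.3.5.1 removes violations from it, including rescue before Day 28 for reasons outside a short list; treatment failure as judged by the investigator is on that list.

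**The concern.** Whether a rescued patient counts as a failure or leaves the analysis is an outcome-related decision. Here it may be made by people who know the arm, and the dose largely gives away OZ439 exposure, the predictor being tested. SAP 2.1.4 defines treatment failure as meeting the early, late clinical or late parasitological criteria. A rescue without those criteria cannot meet that definition, so reviewers have no written standard to apply.

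The primary test rests on few failures, so a handful of decisions can matter. Nothing planned would show their influence. The mITT analyses of PCR-corrected ACPR are descriptive and dose-response only (SAP 2.4.4, 2.4.4.1.2, 2.4.4.1.3). The only planned variation of the primary model is with and without vomiters, and the summary table at the end of SAP Appendix B lists no supportive analysis.

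The choice was foreseeable. For the earlier ferroquine data, Protocol Appendix 8 reports running both options, rescue without failure as failure and as exclusion, and preferring exclusion.

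**Working it through.** **Inputs from Protocol Appendix 8.**
- Test: the OZ439 effect was "analyzed using a 2-sided alpha Wald test at 5" per cent.
- Size and power: "30 evaluable participants per treatment arm will yield a power around 90% to detect an OZ439 concentration effect relation".
- Success rates: simulated rates for "OZ439 at 0, 300, 600 and 1000 mg were of 72%, 81%, 91%, and 97" per cent.
- Model (eq 2): the FQ slope "was fixed at 0.12 by calibration to get ~ 72% success ACPR at Day 28 for FQ 400 mg alone"; for the rest, "the following parameters were extracted from the MMV model": intercept 3.23, OZ439 slope 0.73, log10 parasitemia slope -1.27.
- Baseline log10 parasitemia: normal, mean 4, SD 0.55, truncated at 3.48 and 5.5.

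**Assumptions, not in the documents.** Day 7 concentrations are log-normal with CV 30% to 60% (FQ) and 30% to 100% (OZ439), correlation 0.2, and medians calibrated to the stated success rates. Rescue open to discretion affects 2.5%, 5% or 10% of participants (about 3, 6 or 12 of 120), independently of arm and true outcome. Read these as pre-Day-7 rescues, since only those can change class.

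**1. Expected failures.** 30 × (0.28 + 0.19 + 0.09 + 0.03) = 30 × 0.59 = 17.7 among 120.

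**2. The plan's own power.** In 5,000 simulated trials of 4 × 30, each fitted by logistic regression on FQ, OZ439 and log10 parasitemia with a two-sided 5% Wald test, power is 0.904 at CVs of 30%/30% and 0.918 to 0.921 at wider CVs. The stated figure of around 90% reproduces.

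**3. Where the class changes the outcome** (Per Protocol column):

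| Rescue without WHO criteria | Not a violation | Violation |
|---|---|---|
| Before Day 7 | Failure | Excluded |
| Day 7 or later | Excluded | Excluded |

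**4. Effect of the classification rule.** Same simulation, CVs 40%/50%. False significance means a significant result in favour of OZ439 when it has no effect; the nominal value is 5%/2 = 2.5%. With no discretionary rescue it is 0.018, and power is 0.92.

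| Rule | False significance at 2.5 / 5 / 10% | Power at 2.5 / 5 / 10% |
|---|---|---|
| All failures | 0.019 / 0.021 / 0.023 | 0.80 / 0.69 / 0.53 |
| All excluded | 0.018 / 0.019 / 0.020 | 0.91 / 0.90 / 0.88 |
| Two lower arms failure, two upper excluded | 0.028 / 0.041 / 0.081 | 0.95 / 0.96 / 0.99 |
| Reverse | 0.011 / 0.007 / 0.004 | 0.73 / 0.54 / 0.26 |

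Monte Carlo standard error at 0.041 is √(0.041 × 0.959/5000) = 0.003.

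**5. Single patients.** As individual AUCs are unknown, this uses logit(p) = a + b × dose, with Wald z = b/SE(b) and odds ratios per 100 mg.
- Successes 23/24/26/28 of 30 each: OR 1.149, p = 0.062. Reclassify one failure in each of the two highest arms as a deviation (denominators 30/30/29/29): OR 1.214, p = 0.022.
- Successes 22/24/26/28 of 30 each: OR 1.171, p = 0.034. Do the same in the two lowest arms (29/29/30/30): OR 1.152, p = 0.063.

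The patients moved must be rescues of the discretionary kind.

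**The case against.** The discretion is narrow. It covers investigator-decision rescue only, and from Day 7 the class makes no difference in the Per Protocol column. For missing counts the team may only extend stated rules, and a missing count with malaria fever is always positive.

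A reader might infer that any of the roughly 18 expected failures could be argued out of the analysis. Deleting two or three known failures from Arm A would cut power to 0.82 or 0.74, and deleting them from the 1000 mg arm under no effect would give false positives of 3.7% or 6.6%. The SAP does not allow this: early failure, late clinical failure before Day 7 and recrudescence are fixed as failures, and the case review covers only rescues that met no WHO criterion. Excluding two or three Arm A patients whatever their outcome leaves power at 0.92 or 0.91. Excluding two or three from the 1000 mg arm under no effect gives 1.2% or 1.4%, against 1.5% without exclusions. Exclusion alone does little; the harm needs classification that differs between arms.

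The mITT rules are also immune to the rescue choice, since both classes are failures there. That is a real protection for the descriptive and dose-response results, but it does not extend to the primary exposure-response model.

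These points limit the scope and size. They do not supply the missing criteria, masking or timing.

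**Conclusion.** The gap is real and modest. Unmasked, undated decisions determine whether some pre-Day-7 rescues count as failures or leave the primary analysis, and whether runs of missing counts up to Day 28 are imputed or excluded.

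At an assumed 2.5% or 5% of discretionary rescues and complete arm dependence, false significance in favour of OZ439 is 2.8% or 4.1%, against 1.8% to 2.1% under a uniform rule at those frequencies. The first is barely above the nominal 2.5%, the second clearly above. The opposite pattern lowers power to 0.73 or 0.54. Complete arm dependence is a worst case, the frequency is unknown, and the imputation choice was not quantified.

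It would go too far to infer that the result will be biased, or that any rescue up to Day 28 can be switched. The Day 7 limit itself is an inference: the outcome table has no PK/PD column, and its Per Protocol column is carried over through SAP 2.3.5.1. The Appendix B summary table names the Per Protocol population for the primary analysis, which should be reconciled.

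**What to change.** Amend SAP 2.1.4 and 2.3.5.1 to say that classification of rescue without WHO criteria, and any endorsement of extended imputation, follows written criteria and is finalised before database lock on listings that omit arm, dose and PK data.

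Add two sensitivity runs of the primary model: all pre-Day-7 investigator-decision rescues without WHO criteria as failures, and all excluded.

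A rule that defaults to failure when reviewers disagree is not advised. It conflicts with the exclusion from Day 7 on, and coding such rescues as failures costs power (0.80 against 0.91 for exclusion at 2.5%).

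The cost is a few SAP sentences, the masked listings and two model runs. Masking may be incomplete for reviewers who already know the patients, which is one reason to report both runs. Nothing here bears on when rescue is given.
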